2.7 Study procedures

When a participant is confirmed to be SARS-CoV-2 positive all consenting household members are enrolled and randomised to the same treatment arm. All consenting household members 5 years of age and older will be given the same study treatment. Treatment is 10 days and follow up for primary outcome is 10 days. Follow up for some secondary outcomes are 28 days and outcomes related to long COVID is 6 and 12 months post randomisation.

Daily communication via SMS, online or phone will be conducted by a research team member who will be trained in standard operating procedures as per trial manual. Paediatric or adult swabs (Rhinomed) will be provided to all participants with detailed instructions for self-collection and storage until collected by a research team member. Health care provider collected PCR nasopharyngeal swabs will be collected from all participants prior to commencement of study medication and on day 3, 5 and 10 (+/- 1 day for all time points).

Phone call follow up at day 14 and 28 by a research team member will assess which participants became symptomatic after the initial treatment period and whether participants required hospitalisation during that time. Detailed medical information as to reasons for hospital admission will be sought to confirm if admission was related to COVID-19 infection or for alternative reasons. Research team members will be trained specifically in questions to ask according to trial manual, which will include an escalation process if a research team member believes that additional clinical care is required for the participant or family member.

Telemedicine follow up at day 180 +/- 10 days and day 365 +/- 10 days to ascertain any evidence of long COVID neurological symptoms.

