3.8. Assigning SARS CoV-2 infection status at day 1 and for all outcomes

The following algorithm will be used to determine whether a participant is regarded as positive or negative for SARS CoV-2. In general, only the health care provider collected PCR result will be used to determine infection status. The exception would be when the result was inconclusive.

SARS CoV-2 infection at the time point will be positive if the health care provider collected PCR result is "Detected" and negative if the PCR result is "Not detected".

If the result of the healthcare provider collected swab was inconclusive the following algorithm will be followed:

The result of the self-collected Rhinomed swab collected on the same date as the inconclusive healthcare provider collected swab will determine the final result. If the result of the self-collected Rhinomed swab is "Detected" the result will be positive and if the result is "Not detected" the result will be negative.

If the self-collected Rhinomed swab was also inconclusive, or was missing, the following algorithm will be followed (using the healthcare provider collected swab):

- If the inconclusive result was followed later by a "Detected" result (for example, Inconclusive on Day 3 and Detected on Day 5) then the inconclusive result will be deemed to be positive.
- If the inconclusive result was followed later by a "Not detected" result, then the inconclusive result will be deemed to be negative.
- If the inconclusive result was the last available result, then the inconclusive result will be deemed to be negative.

This algorithm will be used to determine both the primary endpoint (positive on any of Day 3, 5 or 10) and all secondary endpoints related to SARS-CoV-2 positivity.

For the primary objective only, the following two sensitivity analyses will also be done:

Sensitivity analysis 1: Only healthcare provider collected swabs will be used. If the result is inconclusive, it will be regarded as positive.

Sensitivity analysis 2: Only healthcare provider collected swabs will be used. If the result is inconclusive, it will be regarded as negative.

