6. SECONDARY OUTCOMES

For all secondary outcomes referring to SARS-CoV-2 status we will use the algorithm as discussed in Section 3.8 and used for the primary outcome to determine SARS-CoV-2 infection status at any time point.

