6.1 Secondary outcome 1. Efficacy of intranasal heparin to reduce SARS-CoV-2 viral shedding

To test the efficacy of intranasal heparin to reduce SARS-CoV-2 viral shedding over 10 days from day of positive swab (health professional collected swab day 3 and 5, and day 10)

Measure

1.1. Total number of index cases and household contacts combined (nasopharyngeal swab positive on day 1) who remain swab positive on day 3 according to health care provider collected swab

- 1.2. Total number of index cases and household contacts combined (nasopharyngeal swab positive on day 1) who remain swab positive on day 5 according to health care provider collected swab
- 1.3. Total number of index cases and household contacts combined (nasopharyngeal swab positive on day 1) who remain swab positive on day 10 according to health care provider collected swab

Estimand

Population: Household members who tested positive for SARS CoV-2 on day 1 on a nasopharyngeal swab PCR testing (health care provider collected swab)

Treatment: Initially randomised intervention to unfractionated intranasal heparin 1400u each nostril (as heparin solution 5,000u/ml, 140microL/actuation, TWO actuations each nostril) THREE times daily via a plastic nasal inhalator device or saline control and any subsequent deviations to the per protocol use of the intervention over 10 days

Outcome: Three different analyses will be done with 3 different outcomes

- a) Testing positive for SARS-CoV-2 by PCR on day 3 (using health care provider collected swab)
- b) Testing positive for SARS-CoV-2 by PCR on day 5 (using a health care provider collected swab)
- c) Testing positive for SARS-CoV-2 by PCR on day 10 (using a health care provider collected swab)

Summary measure: Both relative (risk ratio) and absolute differences (risk difference) in proportions will be reported with 95% confidence intervals

Potential intercurrent events:

Index case in the household not taking study drug. This is defined as compliance <90% Participant (this household member) not taking study drug. This is defined as compliance <90% Either participant (this household member) or index case stop treatment due to adverse event Participant hospitalisation during first 10 days (removed from household) Participant received an anti-viral

Strategy for handling intercurrent event:

All intercurrent events will be handled through the treatment policy strategy, which means that the intercurrent events will be ignored.

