The same analysis as described in Section 5.1 for the primary outcome will be done. We will do the same sensitivity and supplementary analysis, but no subgroup analyses are planned.

Measure

1.4. Time to swab negative based on health care provider collected nasal swab for household members index cases and household contacts) who were swab positive on day 1 by PCR

Estimand

Population: Household members who tested positive for SARS CoV-2 on day 1 on a nasopharyngeal swab PCR **Treatment**: Initially randomised intervention to unfractionated intranasal heparin 1400u each nostril (as heparin solution 5,000u/ml, 140microL/actuation, TWO actuations each nostril) THREE times daily via a plastic nasal inhalator device or saline control and any subsequent deviations to the per protocol use of the intervention over 10 days

Outcome: Days from randomisation to the date of the first negative nasal swab. Participants who still test positive on day 10 will be censored on day 10 and regarded as not testing negative.

Summary measure: Median time to first negative test in each treatment arm. Hazard ratio.

Potential intercurrent events:

Index case in the household not taking study drug. This is defined as compliance <90% Participant (this household member) not taking study drug. This is defined as compliance <90% Either participant (this household member) or index case stop treatment due to adverse event Participant hospitalisation during first 10 days (removed from household) Participant received an anti-viral

Strategy for handling intercurrent event:

All intercurrent events will be handled through the treatment policy strategy, which means that the intercurrent events will be ignored.

Days to first negative test will be calculated from baseline to the first negative PCR tests within the first 10 days after randomisation. Participants who still test positive at the last time point will be censored at the time

of last test. Participants who are lost to follow-up without testing negative, will be censored at the time of the last positive test. The days to negative test will be compared between the two treatment arms using a proportional hazards models with clustered standard errors [using vce(cluster) in Stata]. The model will be adjusted for the same set of defined baseline covariates (Section 5.1). Days to negative test will be summarised by reporting the median, with 95% confidence interval.

Measure

1.5 Mean Ct values on days 3, 5 and 10

Estimand

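### An unresolved inconclusive last swab is coded negative and so counts as viral clearance in the shedding measures, while Sections 3.8 and 6.1 disagree on whether this coding is tested

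*SAP*

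**What the plan says.** SAP Section 3.8 assigns infection status from the provider-collected PCR swab. If that swab is inconclusive, the self-collected Rhinomed swab of the same date decides. The next step is conditional: "If the self-collected Rhinomed swab was also inconclusive, or was missing, the following algorithm will be followed". A later Detected provider result then makes the inconclusive swab positive, and a later Not detected result makes it negative. The last branch reads: "If the inconclusive result was the last available result, then the inconclusive result will be deemed to be negative".

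The algorithm covers the primary endpoint and "all secondary endpoints related to SARS-CoV-2 positivity". Section 6 repeats this: "For all secondary outcomes referring to SARS-CoV-2 status we will use the algorithm as discussed in Section 3.8".

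Measures 1.1 to 1.4 (Section 6.1) concern household members who were PCR positive on day 1. Measures 1.1 to 1.3 are positivity on days 3, 5 and 10. Measure 1.4 is time to the first negative swab. Under Section 2.7, day 10 is the last routine provider swab.

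On sensitivity analyses, Section 3.8 introduces the inconclusive-as-positive and inconclusive-as-negative codings with: "For the primary objective only, the following two sensitivity analyses will also be done". Section 6.1 closes its text on Measures 1.1 to 1.3 with: "We will do the same sensitivity and supplementary analysis, but no subgroup analyses are planned".

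**The concern.** Defaulting an unresolved result to negative is a natural choice for the primary outcome, where participants start negative and the event is a new infection. In the shedding measures participants start positive, and a negative result is the favourable outcome. The last branch looks only forward in time. It ignores a Detected result on the preceding swab and can record clearance that no swab has shown.

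Two things are at stake. In Measure 1.4 some events may rest on no Not detected result, which sits badly with that measure's own censoring rule. And because two sections disagree on whether the alternative codings apply to Measures 1.1 to 1.3, an analyst could decide after seeing the results whether to report them.

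**Working it through.** The plan gives no figure on this point to reproduce. The check follows the rules through example participants, then shows what the coding can do to the comparison.

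**Step 1. A participant followed to day 10.** Provider swabs are Detected on days 1, 3 and 5 and inconclusive on day 10; the day 10 self-swab is missing or inconclusive.
- Section 3.8: no later swab exists, so day 10 is negative.
- Measure 1.3: not positive on day 10, so counted as cleared.
- Measure 1.4: no earlier negative, so day 10 is the first negative swab and an event.
- Not detected results on record: none.

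**Step 2. A participant lost early.** Provider swabs are Detected on days 1 and 3 and inconclusive on day 5, with no conclusive self-swab; the participant is then lost.
- Section 3.8: the day 5 swab is the last available, so it is negative.
- Measure 1.2: counted as cleared. (If the last swab were day 3, this would happen in Measure 1.1.)
- Measure 1.4: an event on day 5. Yet Section 6.1 censors people lost without a negative test at their last positive test, here day 3. The outcome depends on whether the recoded swab counts as having tested negative.

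**Step 3. Effect on the day 10 comparison.** For heparin (H) and placebo (P), let *d* be the proportion classified positive without using the last branch, and *q* the proportion left unresolved and so sent to that branch.
- Coded negative: proportion positive = *d*; RD = *d*_H − *d*_P.
- Coded positive: proportion positive = *d* + *q*; RD = (*d*_H − *d*_P) + (*q*_H − *q*_P).
- Gap between the codings = *q*_H − *q*_P.

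The SAP gives no value of *q*, so these are assumptions:

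| *q* heparin | *q* placebo | Gap in RD | Coding as negative favours |
|---|---|---|---|
| 3% | 3% | 0 points | neither; clearance up by up to 3 points in both arms |
| 7% | 3% | 4 points | heparin |
| 8% | 2% | 6 points | heparin |
| 3% | 7% | 4 points | placebo |

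These gaps are upper bounds on the bias, because some unresolved swabs will come from people who had truly cleared.

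**Step 4. The same on the ratio scale.** Assume *d* + *q* = 40% in both arms.
- *q* = 10% heparin, 5% placebo, coded negative: 30% / 35% = 0.86.
- Coded positive: 40% / 40% = 1.00.
- Imbalance reversed, coded negative: 35% / 30% = 1.17.
- With *d* + *q* from 30% to 50%, the first ratio runs from 20/25 = 0.80 to 40/45 = 0.89, and the reversed one from 25/20 = 1.25 to 45/40 = 1.125.

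With equal *q* the risk difference is the same under both codings. The risk ratio stays at 1 if the arms do not differ, though its size depends on the coding if they do.

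**Step 5. Which sensitivity analyses apply.**

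| Measure | Section 3.8 | Section 6.1, read with 5.2 |
|---|---|---|
| Primary | both codings | both codings (5.2, items 3 and 4) |
| 1.1 to 1.3 | excluded | same as primary, so both codings |
| 1.4 | excluded | none stated |

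The Section 6.1 sentence stands before Measure 1.4, whose own text adds no such check. The table shells do not settle the conflict: Table 10 has no rows for the two codings, but neither does Table 8 for the primary outcome, where they are certainly planned.

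**The case against.** The rule is explicit and identical in both arms. It bites only when three things coincide: an inconclusive provider swab, no conclusive self-swab from that date, and no later conclusive provider swab. Self-collection swabs are given to all participants, so many cases should be resolved earlier. For days 3 and 5 a later swab will usually decide. Coding such swabs positive is no more correct than coding them negative: if heparin brings viral load close to the detection limit, extra inconclusive results may reflect a real effect that positive coding would hide. Read literally, Section 6.1 already provides both codings for Measures 1.1 to 1.3, and Measure 1.5 compares Ct values on the same days.

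Most of this stands, and it rules out stronger readings that a reader might infer:
- That Section 3.8 always leans toward clearance. The self-swab step and the later-Detected branch can both return positive; only the last branch defaults to negative.
- That the bias favours heparin. This needs more unresolved results on heparin, and the SAP gives no rates. Nothing in it shows that the spray disturbs the assay or the sampling.
- That 4 or 6 points can be judged against the 10-point difference used for sample size (85% versus 75%). That difference concerns transmission to household contacts, a different population and outcome.

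The objection does not answer two points. Measure 1.4 can record a negative event with no Not detected result, and Sections 3.8 and 6.1 cannot both be followed for Measures 1.1 to 1.3.

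**Conclusion.** The point holds within limits. For day 1 positives, an unresolved inconclusive last swab is counted as clearance in Measure 1.3 (or in 1.1 or 1.2 if the participant is then lost) and, with no earlier negative, as an event in Measure 1.4. This raises apparent clearance in both arms. The risk difference moves only if unresolved inconclusives are unequal between arms, in either direction, by at most the difference in their rates: up to 4 points for an assumed 3% versus 7%. The true size is unknown.

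The conflict between Sections 3.8 and 6.1 over Measures 1.1 to 1.3, and the lack of any stated check for Measure 1.4, do not depend on an assumed rate. Only secondary outcomes are affected. The text should be corrected before the arms are compared. The documents do not show that the main analysis of Measures 1.1 to 1.3 must switch to coding these swabs positive.

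**What to change.** 1. In Section 3.8, change the scope of the two inconclusive-result analyses from the primary objective alone to the primary outcome and Measures 1.1 to 1.4. For 1.1 to 1.3 this reconciles 3.8 with 6.1; for 1.4 it adds a new analysis, and Section 6.1 should say so.
2. In Measure 1.4, do not count an unresolved inconclusive last swab as a negative event. Censor the participant at the last conclusive positive swab, in line with the existing rule for those lost without a negative test.
3. For Measures 1.1 to 1.3, report the results under both codings and add the rows to Table 10.
4. Tabulate unresolved inconclusive swabs by arm and day, so that a reader can see whether the coding could matter.

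The cost is SAP wording, one recode, a little more analysis work and slightly fewer events in Measure 1.4.

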3.9. Baseline covariate set

A set of covariates which will be included in models for all primary and secondary outcomes (unless specified otherwise) are: stratification factors (time from positive test to randomisation (binary)) and whether the index case is a child < 5 years(binary), participant age (continuous), inhaled steroid use at baseline (binary), days since symptom onset for index case at randomisation (continuous), whether there are children in the household (binary) and household size (continuous). This is referred to as the baseline covariate set.

Some of these covariates are correlated with each other and may also have sparse data in some of the cells, which may lead to convergence problems with the models. If that is the case, we will exclude some of the baseline covariate set until we can get a model that converges. We will first exclude the sparsest variables, and secondly exclude the variables most correlated with other variables.

We will also repeat each analysis with a model including only the two stratification variables.

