2.6 Sample size

For the primary research outcome, a sample size of 120 index cases per arm will provide 80% power. We anticipate that the attack rate for within household transmission will be approximately 85% in the control arm and 75% in the intervention arm. Under these assumptions, in a cluster randomised trial with a binary outcome, assuming an intracluster correlation coefficient of 0.2, an alpha of 0.05 (two sided), and assuming 3 additional household members (in addition to the index case) we have 80% power to detect a reduction in transmission to household contacts. The requisite sample size is then 120 index cases and 360 household contacts per arm. Allowing for 10% loss to follow-up this is increased to 134 index cases (households) per arm, approximately 536 persons per arm. We plan to enroll 268 households and approximately 1072 individuals.

If the household size is 2 additional people, rather than 3, and with all other assumptions the same, we would require 334 households and approximately 1002 individuals. The target sample size for the primary outcome is 1100 individuals enrolled.

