4.2. Baseline characteristics

The following variables will be summarised at baseline by treatment arm. Categorical variables will be summarised as the number and percentage, and continuous variables as mean, standard deviation (SD) and range (minimum and maximum) or median and interquartile range (IQR) when continuous data is skewed.

Household information: Household size, number of children in household, household type, number of bathrooms, number of bedrooms, number of household members enrolled.

Index case information: Time of positive test collection, index case <5 years old, age, interpreter required, sex, COVID-19 vaccine history (number of doses received), had COVID-19 before (number of infections), COVID-19 symptoms present (yes/no and fever or chills, cough, shortness of breath, fatigue, muscle or body aches, headache, loss of taste or smell, sore throat, congestion or runny nose, nausea or vomiting, diarrhea), number of days with symptoms, nasal spray use

Household member information: Age, interpreter required, SARS-CoV-2 status at screening, sex, COVID-19 vaccine history (number of doses received), had COVID-19 before (number of infections), COVID-19 symptoms present (fever or chills, cough, shortness of breath, fatigue, muscle or body aches, headache, loss of taste or smell, sore throat, congestion or runny nose, nausea or vomiting, diarrhea)

Demographic data at baseline will be provided for the household, index case and household members. For household members, the demographics will be provided overall, as well as by SARS-CoV-2 status.

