5.4. Subgroup analyses

The following subgroup analyses will be done:

Age: <5, 5-<18, 18-65, >65 years

Anti-viral treatment: Use of anti-viral treatment by the index case at randomisation. These include Paxlovid, Molnupiravir, Remdesivir and Favipiravir.

Number of SARS-CoV-2 exposures (vaccinations and infections) prior to the trial: 4 or less, vs > 4 Use any nasal treatment prior to coming into trial (Carrageenan or inhaled steroid, variables cm_flonasalspray_yn and cm_inhaledsteroids_yn)

Number of people in house: 2-3 vs > 3

Ratio of people to be drooms: < 1, 1, > 1

The subgroup analysis will be done by including an interaction term between the treatment arm and the subgroup in the model described in Section 5.1. For example,

xtpoisson outcome i.arm##i.subgroup baseline_covariates, re vce(robust) irr

The p-value of the subgroup by arm interaction term will be assessed to determine whether there could be a subgroup effect, with the understanding that the analysis is probably underpowered.

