Index case in the household not taking study drug. This is defined as compliance <90% Participant (this household member) not taking study drug. This is defined as compliance <90% Either participant (this household member) or index case stop treatment due to adverse event Participant received an anti-viral

Strategy for handling intercurrent event:

All intercurrent events will be handled through the treatment policy strategy, which means that the intercurrent events will be ignored.

The same analysis as described for Measure 4.3 will be done.

This analysis will also be repeated in the subgroup of participants who had SARS-CoV-2 infection.

The following subgroup analyses will be done:

Age: Younger than 65 vs 65 and older

Pre-existing mental health problems: This will be measured by self-reported current comorbidities as mental health disorder (variable mhcat____18).

Previous SARS-CoV-2 infections: Any vs none

These subgroup analyses will be done by including an interaction term between the treatment arm and the subgroup in the model described for Measure 4.3. For example, using the Stata code mixed outcome i.arm##i.subgroup baseline_covariates || household:

The p-value of the subgroup by arm interaction term will be assessed to determine whether there could be a subgroup effect, with the understanding that the analysis is probably underpowered.

Measure 5.1.3

In addition to assessing whether treatment assignment was associated with neurological long COVID we want to investigate whether neurological long COVID outcomes were different for participants who tested positive for SARS-CoV-2 vs those who tested negative.

Estimand

Population: Household members (older than 5 years) enrolled in the study, regardless of SARS-CoV-2 infection status (all enrolled participants)

Exposures compared: Tested positive for SARS-CoV-2 any time during the study (baseline positive or positive during the trial) vs tested negative for SARS-CoV-2 at all time points

Outcome: Ordinal Likert scale measurement of severity of each of the symptoms listed in Measure 5.1.1. at 6 months, with a 2 month window (i.e. including outcomes measured between 4 and 8 months)

Summary measure: The overall odds ratio will be reported with 95% confidence interval

Potential intercurrent events: None

Strategy for handling intercurrent event: Not applicable

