We will summarise the number of participants in each of the 4 categories of the Likert scale in each exposure group. A proportional odds logistic regression will be used to calculate the overall odds ratio, adjusted for the stratification variables and randomised arm and clustered on household. The assumption of proportional odds

will be investigated. If it is violated, we will fit a multinomial regression and calculate an odds ratio for each category.

Measure 5.1.4

In addition to assessing whether treatment assignment was associated with neurological long COVID we want to investigate whether neurological long COVID outcomes were different for participants who tested positive for SARS-CoV-2 vs those who tested negative. The research question is: Does testing positive for SARS-CoV-2 at baseline or during the 10 days of active treatment increase the severity of long COVID symptoms at 6 months?

Estimand

Population: Household members (older than 5 years) enrolled in the study, regardless of SARS-CoV-2 infection status (all enrolled participants)

Exposures compared: Tested positive for SARS-CoV-2 any time during the study (baseline positive or positive during the trial) vs tested negative for SARS-CoV-2 at all time points

Outcome: Continuous neurological long COVID score (described above) at 6 months, with a 2 month window (i.e. including outcomes measured between 4 and 8 months)

Summary measure: The mean difference between SARS-CoV-2 infected and uninfected participants will be reported with 95% confidence interval

Potential intercurrent events: None

Strategy for handling intercurrent event: Not applicable

The two exposures will be compared using mixed effects linear regression with neurological long COVID score as the outcome, adjusting for stratification factors (time from positive test to randomisation, whether the index case is a child < 5 years) randomised treatment arm and the defined baseline covariate set, with household as random effect to take the clustering by household into account.

The mean difference between the exposures will be calculated in Stata as follows using a mixed effects GLM with random intercepts:

mixed outcome i.infection_status i.arm baseline_covariates || household:

Measure 5.1.5

For participants over 16 years of age, cognition and mood were assessed using the harmonised procedures developed by the Neuro-COVID Neuropsychology International Task force. Included measures were:

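### The infected-versus-uninfected long COVID comparisons (Measures 5.1.3, 5.1.4, 5.1.6 and their 12-month repeats) leave out recorded likely confounders: prior SARS-CoV-2 exposure, sex and pre-existing mental health disorder.

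*SAP*

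**What the plan says.** Section 3.9 introduces the set as "A set of covariates which will be included in models for all primary and secondary outcomes (unless specified otherwise) are: stratification factors". The factors are time from positive test to randomisation and index case under 5. The other members are participant age, inhaled steroid use, days since the index case's symptom onset, children in the household, and household size. Section 5.1 repeats the list for the primary model.

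Other sections show what else is recorded:

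- Section 4.2 lists "COVID-19 vaccine history (number of doses received), had COVID-19 before (number of infections" among the baseline variables, for index cases and for household members, together with sex.
- Section 5.4 makes prior exposure a subgroup variable for the primary outcome: "Number of SARS-CoV-2 exposures (vaccinations and infections) prior to the trial: 4 or less, vs > 4".
- Section 6.5 uses previous infection (any or none) as a subgroup variable for fatigue and for the total long COVID score, and also "Pre-existing mental health problems: This will be measured by self-reported current comorbidities as mental health disorder".

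Section 6.5 then defines three measures that compare people who tested positive at any time in the study with people who tested negative throughout. Measure 5.1.4 poses its research question, for the 6-month assessment, in these words: "Does testing positive for SARS-CoV-2 at baseline or during the 10 days of active treatment increase the severity of long COVID symptoms". Measure 5.2 repeats all the analyses at 12 months.

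**The concern.** In Measures 5.1.3, 5.1.4 and 5.1.6 the exposure is infection status, which nobody assigned. The adjustment set therefore has to do the work that randomisation does elsewhere in the plan. The 3.9 set looks chosen for transmission and for the arm comparison; nothing in it describes the participant's own immunity or prior health apart from age and inhaled steroid use.

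People who stay negative in an exposed household may well differ in vaccination and past infection from those who become positive. The same history may affect symptoms 6 or 12 months later. Pre-existing mental health disorder matters most for Measure 5.1.6, which analyses the DASS depression, anxiety and stress scales. If these variables differ between the groups, the reported odds ratios and mean differences are not the effect of infection that 5.1.4 asks about, and a larger sample would not help.

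**Working it through.** **1. The plan's own figures.** Section 2.6 gives these inputs: "We anticipate that the attack rate for within household transmission will be approximately 85% in the control arm and 75% in the intervention arm"; "assuming an intracluster correlation coefficient of 0.2, an alpha of 0.05 (two sided"; "assuming 3 additional household members (in addition to the index case"; 80% power.

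- Two proportions, 0.85 against 0.75: 250 per arm.
- Design effect: 1 + (3 − 1) × 0.2 = 1.4.
- Households: 250 × 1.4 / 3 = 117 per arm, against the plan's 120 (within 3%).
- Loss to follow-up: 120 / 0.9 = 134 per arm, so 268 households and 268 × 4 = 1072 people. This matches.
- Two contacts per household: 250 × 1.2 / 2 = 150; 150 / 0.9 = 167 per arm, so 334 households and 1002 people. This matches.

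The sample size reproduces and is not affected by this point.

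**2. The three models side by side.**

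| Measure | Outcome | Adjusted for | Prior exposure, sex, mental health disorder |
|---|---|---|---|
| 5.1.3 | Each symptom, ordinal | Stratification variables, arm | None |
| 5.1.4 | Total score, 0 to 66 | Arm, 3.9 set | None |
| 5.1.6 | Cognition and mood scales | 3.9 set, through 5.1.5 and then 4.3 | None |

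The model reached from 5.1.6 has arm as its comparison term. The SAP does not say whether arm stays in once infection status is the exposure.

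**3. The comparison group.** With 268 households and 3 contacts each there are 804 contacts. At a mean attack rate of (85% + 75%) / 2 = 80%, about 0.20 × 804 = 161 stay uninfected, or 161 / 1072 = 15% of participants. The reference group is a small, selected minority who escaped infection at home.

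**4. Illustrative bias from prior exposure.** The SAP gives no strength for any covariate, so these are assumptions: high prior exposure in q = 50% of contacts; infection risk lower by d in that group; overall risk p = 0.80; later score shifted by g SD.

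- Difference in prevalence of high exposure, uninfected minus infected: d × q(1 − q) / [p(1 − p)] = d × 0.25 / 0.16.
- For d = 0.10 this is 0.156; for d = 0.20 it is 0.312.
- Absolute bias = g × that difference.

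| d | g = 0.1 SD | g = 0.2 SD | g = 0.3 SD |
|---|---|---|---|
| 0.10 | 0.016 | 0.031 | 0.047 |
| 0.20 | 0.031 | 0.062 | 0.094 |

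The direction is open. If prior exposure lessens later symptoms, the contrast overstates the harm of infection; if past infections leave symptoms of their own, it understates it. The calculation covers contacts only. The real infected group also contains index cases, whose exposure history cannot be guessed from the SAP.

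**5. Primary model, precision only.** Let r be the within-household correlation of exposure. The share of household-mean variance removed is d² × 0.25 × (1 + 2r) / (0.16 × 1.4). Power at 120 households of 3 contacts per arm, without the covariate, is 81.1%.

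| d | Variance removed, r from 0 to 1 | Power |
|---|---|---|
| 0.05 | 0.3 to 0.8% | 81.2 to 81.4% |
| 0.10 | 1.1 to 3.3% | 81.5 to 82.4% |
| 0.20 | 4.5 to 13.4% | 82.8 to 86.3% |

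A simulation with a Poisson model and cluster-robust standard errors (1000 runs per setting) gave model-based variance ratios of 0.98 to 0.99 for d = 0.10 and 0.92 to 0.95 for d = 0.20. The mean risk ratio was about 0.88 with or without the covariate.

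**The case against.** **The primary analysis.** A reader might infer that leaving prior exposure out of section 3.9 biases the primary result or seriously weakens it. The documents do not support that. Arm is randomised by household, so omitting a prognostic covariate is a design choice about precision. The set is pre-specified, and the plan repeats each analysis with the stratification variables only. Chance imbalance in exposure is not a further harm either, because it is already inside the standard error. With the plan's 360 contacts per arm and design effect 1.4 (assuming exposure clusters to the same degree), the imbalance SD is √(2 × 0.25 × 1.4 / 360) = 4.4 points. At d = 0.10 that moves the risk difference by about 0.4 points, against a standard error of √[(0.1275 + 0.1875) × 1.4 / 360] = 3.5 points. This objection stands in full.

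**Subgroup status.** Being a subgroup variable does not oblige a covariate. Section 5.4 also lists index-case antiviral use and the ratio of people to bedrooms, and neither is in the 3.9 set. Testing whether previous infection modifies the heparin effect does not show that it affects who becomes infected. This stands as logic. The case for adjustment rests on the non-randomised contrast; the subgroup lists show only that the data exist.

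**Size.** The bias figures are assumed and small, and the measures are secondary. That limits the weight of the point but does not remove it, since Measure 5.1.4 asks a causal question and the data are at hand.

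**Availability.** A reader might also infer that exposure history is held for everybody. Section 4.2 lists it for index cases and household members. Section 2.3 also lets people outside the trial contribute COVID-19 status alone, and the SAP does not say that their history is recorded.

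**Conclusion.** The point holds for the infected-versus-uninfected comparisons. Measures 5.1.3, 5.1.4 and 5.1.6, and their 12-month repeats, estimate a non-randomised contrast without adjusting for prior exposure, sex or pre-existing mental health disorder, although the SAP lists all three as recorded. The gap is certain from the text. The size of the resulting bias is not: 0.02 to 0.09 SD for prior exposure depends on assumed values of d, g and q, and no comparable figure for sex or mental health disorder can be derived from the document.

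It would be tempting to treat section 3.9 as the single source of the problem. It is not, because 5.1.3 does not use that set, so amending 3.9 alone would leave the least adjusted of the three comparisons unchanged.

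For the primary model there is no bias to correct. The possible gain is about 0 to 3% of variance for risk differences up to 10 points, and less after overlap with age, which is already in the model.

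**What to change.** **Main change.** Write one explicit confounder set into each of Measures 5.1.3, 5.1.4 and 5.1.6 and their repeats under 5.2:

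- the 3.9 set and randomised arm;
- number of prior exposures (vaccine doses plus infections), without a separate any-or-none infection term, which would overlap with the count;
- sex;
- pre-existing mental health disorder.

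Write the 5.1.6 model out in full instead of by cross-reference, with infection status as the exposure term. State whether the 3.9 rule for dropping covariates applies to these models; it removes the sparsest terms first, which could take out a confounder. If the sponsor prefers not to adjust, the alternative is to label these comparisons descriptive and reword the causal question in 5.1.4.

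**Optional.** Add the continuous exposure count to the 3.9 set for the primary model. The SAP gives no reason to remove inhaled steroid use to make room for it.

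**Cost.** This is a wording change using variables the SAP already lists. It adds one to three parameters beyond the 3.9 set and arm. Participants with a missing covariate would drop out of a complete-case model, and section 3.7 triggers imputation on missing outcomes only. Status-only household members are the likeliest gap. They bear mainly on the optional primary-model change, because the long COVID populations are enrolled participants; there, a few percent missing could cancel the small precision gain.
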